Does this trial meet the definition of an Applicable Clinical Trial and require registration on ClinicalTrials.gov? Yes

Who will be responsible for registering and maintaining the registration of this Applicable Clinical Trial? The BCM PI will register the trial because either:

- the trial is BCM PI-initiated,
- BCM is the lead site of this multicenter trial, or,

- the industry sponsor has instructed the BCM PI to register the trial, or,
- registration of this trail is required as a term and condition of the reward by the funding agency.

ClinicalTrials.gov Identifier:

NCT

Section B: Exempt Request

B. Exempt From IRB Review

Not Applicable

Section C: Background Information

The Focused Assessment of Sonography for Trauma (FAST) is a rapid point-of-care ultrasound exam performed on blunt and penetrating trauma patients who are too critically injured to be transported to a CT scanner. In performing this exam, time to acquisition of adequate images is crucial to clinical decision-making as patients undergoing this exam have a high probability of deteriorating if not intervened on appropriately.

Low-frequency ultrasound is used to image the abdominal cavity in these patients, using either a curvilinear transducer (colloquially, an "abdominal probe") or a phased-array transducer (a "cardiac probe"). Both of these transducers are capable of acquiring the images necessary to interpret a FAST exam, but it has not been studied whether using one transducer instead of the other improves time to image acquisition or image quality.

Section D: Purpose and Objectives

This protocol will evaluate whether there is a difference in the speed or quality with which emergency medicine residents and medical students are able to acquire images for the FAST exam depending on the type of transducer (curvilinear or phased array) they use for the exam.

Section E: Protocol Risks/Subjects

E1. Risk Category

Category 1: Research not involving greater than minimum risk.

E2. Subjects

Gender:

Both

Age:

Adult (18-64 yrs)

Ethnicity:

All Ethnicities

Primary Language:

English

Groups to be recruited will include:

Healthy, non-patient, normals

Which if any of the following vulnerable populations will be recruited as subjects?

Employees or lab personnel, Women of child bearing potential

Vulnerable populations require special protections. How will you obtain informed consent, protect subject confidentiality, and prevent undue coercion?

Our population, which includes both subjects that will perform the exam and will have the exam performed on them, will include women of child bearing potential. However, abdominal and cardiac ultrasonography is generally recognized as safe, with no known long-term adverse health effects. We do not anticipate a negative effect of the performance of these ultrasound exams on the health of our subjects or their future child-bearing potential. Human model patients who are pregnant will be excluded from the study.

We will be recruiting residents and faculty in this study. Study participation and data will not affect participant evaluations or consideration of employment status and this will be reflected on the written informed consent. We will take measures to de-identify the study data and prevent future re-identification of the study data. We will not recruit individuals who have limited decision-making capacity.

E3. Pregnant woman/fetus

Will pregnant women and/or fetuses (as described in 45 CFR 46 Subpart B) be enrolled in the research?

E4. Neonates

Will neonates of uncertain viability or nonviable neonates (as described in 45 CFR 46 Subpart B) be enrolled in the research?

No

E5. Children

Will children be enrolled in the research?

No

Section F: Design/Procedure

F1. Design

Select one category that most adequately describes your research:

c) Pilot

Discuss the research design including but not limited to such issues as: probability of group assignment, potential for subject to be randomized to placebo group, use of control subjects, etc.

Participants will be block-randomized to a group A and group B. For the purposes of this text, the term "operators" will refer to the participants who are performing the ultrasound exam. The term "patients" will refer to the healthy volunteers with no medical conditions who will have the ultrasound exam performed on them.

Group A will conduct an ultrasound exam on one patient using a curvilinear transducer, and group B performs the exam on another different patient using a phased-array transducer. After each operator performs their examination, they will cross-over, performing the same exam using the other transducer on the other patient.

Inclusion Criteria:

Emergency medicine residents (PGY 1-3), emergency medicine PA fellows, and emergency medicine faculty at Baylor College of Medicine will be recruited as operators. Healthy, non-pregnant emergency medicine faculty members recruited from Baylor College of Medicine who sign a written informed consent to be the subjects of the ultrasound examination will be used as the model patients.

Exclusion Criteria:

Pregnant women, adults over age 64, individuals younger than 18, and any individuals who elect not to participate or who withdraw their consent at a later date.

F2. Procedure

The FAST exam is part of standard clinical care of the trauma patient and consists of four views of the thorax and abdomen acquired with an ultrasound transducer. These views are: subxiphoid images of the heart; right upper quadrant images of the hepato-renal recess and right paracolic gutter; left upper quadrant images of the spleen-diaphragm interface, spleno-renal recess, and left paracolic gutter; and suprapubic images of the bladder and recto-vesicular or recto-vaginal pouch. Each operator will perform two ultrasound exams each with a different type of ultrasound transducer. The performance of ultrasound exams is part of standard clinical training of emergency medicine practitioners and medical students, and is considered a procedure with minimal risk to both the operator and patient. No part of the actual ultrasound exam being performed that is described here is investigational; all parts of this exam, performed with either the phased array or curvilinear probe, are considered the current standard of care for unstable trauma patients.

Prior to the ultrasound procedure we will administer a pre-survey to each participant. This survey will assess their knowledge of the adequate views of the FAST exam, their level of experience with the use of curvilinear and phased array probes, and their general level of ultrasound experience.

Each patient will be fasted for three hours prior to the exam.

Operators randomized to group A will perform an ultrasound exam on a patient using a phased-array transducer, and operators randomized to group B will perform an exam on the other patient using a curvilinear transducer. Both exams will be a complete FAST exam and each of the four exam components will be timed. After each subject in each group completes their FAST exam, they will cross-over.

The time to complete image acquisition of each of the four parts of the FAST exam will be collected for each subject with each transducer. The ultrasound images acquired for each transducer and each view will also be evaluated to assess them for quality of the acquired images, which will be graded as either adequate (sufficient for interpretation in a real patient) or inadequate (insufficient for interpretation in a real patient).

Section G: Sample Size/Data Analysis

G1. Sample Size

How many subjects (or specimens, or charts) will be used in this study?

Local: 40 Worldwide: 40

Please indicate why you chose the sample size proposed:

This is a convenience sample of the number of expected residents, PA fellows, and faculty that we expect to participate.

G2. Data Analysis

Provide a description of your plan for data analysis. State the types of comparisons you plan (e.g. comparison of means, comparison of proportions, regressions, analysis of variance). Which is the PRIMARY comparison/analysis? How will the analyses proposed relate to the primary purposes of your study?

Time to completion of each part of the ultrasound exam, total time to completion of the ultrasound exam, and whether or not the ultrasound exam is adequate or inadequate is the dependent variable. The independent variable is the type of ultrasound transducer (curvilinear or phased array) used for the ultrasound exam. The mean values of the time to completion will be compared in this data analysis and analyzed for significance, and whether or not the exam was adequate or inadequate will be compared (through a Fisher's exact test) to determine if there is a significant difference between the curvilinear transducer and the phased array transducer groups.

The primary comparison/analysis is the time to exam completion. The secondary comparison/analysis is

whether or not the exam was adequate. This analysis will determine if the hypothesis of the study, that there is a significant difference in time to completion and adequacy of the ultrasound exam, is supported or refuted.

Section H: Potential Risks/Discomforts

H1. Potential Risks/Discomforts

Describe and assess any potential risks/discomforts; (physical, psychological, social, legal, or other) and assess the likelihood and seriousness of such risks:

This protocol does not include exposure to ionizing radiation.

There are several risks for discomfort.

For the operators (subjects performing the exam), discomforts are primarily related to a loss of confidentiality in their results: having their times to completion or adequacy of the exam revealed to third parties. The likelihood of these risks is small, as we will securely store identifying research data in accordance with BCM policies and we will not disclose or report any identifiable research data outside of the study investigators.

For the patients (healthy volunteers having exams performed on them), discomforts may be related to: mild discomfort from having the ultrasound transducer pressed against the body during the examination, and social discomfort as they will have to partially expose their abdomen to undergo the portions of the FAST exam. Additionally, there may be a discomfort related to loss of confidentiality about participating in the study, and there is a small risk of the discovery of an incidental finding in each model patient.

There is very little risk of long-term damage or pain caused by the pressing of the ultrasound transducer against the body. The likelihood of social discomfort from disrobing depends on the individual comfort level of the subject. We will inform subjects of this risk, take care to ensure that they are adequately covered with sheets and clothing during the exam to protect their bodily privacy, and ensure that they are comfortable voicing any concerns or stopping the exam if necessary. The risk of confidentiality loss is small as we will take measures to secure identifiable data. Finally, there is a risk of the discovery of an incidental finding in the healthy model patients (for example the discovery of a renal cyst or abnormal abdominal fluid collection). This risk is inherent to the performance of any ultrasound exam. It is difficult to predict if patients will have incidental findings if they are otherwise healthy. Any incidental findings that are noted on the ultrasound exam by the PIs will be confidentially shared with the patient and they will be counseled to follow up on these findings as soon as possible with their physician.

H2. Data and safety monitoring plan

Do the study activities impart greater than minimal risk to subjects?

H3. Coordination of information among sites for multi-site research

Is the BCM Principal Investigator acting as the SPONSOR-INVESTIGATOR for this multi-site research? No or Not Applicable

Is BCM the COORDINATING CENTER for this multi-site research?

No or Not Applicable

Section I: Potential Benefits

Describe potential benefit(s) to be gained by the individual subject as a result of participating in the planned work. There is no potential benefit to each individual subject from this study.

Describe potential benefit(s) to society of the planned work.

The potential benefit to society is determining whether the choice of ultrasound transducer during the performance of this common ultrasound exam affects its performance or time to completion.

Do anticipated benefits outweigh potential risks? Discuss the risk-to-benefit ratio.

The anticipated benefits to society outweigh the risks to the subjects. There is no more than minimal risk to each individual subject related to the performance of a non-invasive ultrasound exam.

Section J: Consent Procedures

J1. Waiver of Consent

Will any portion of this research require a waiver of consent and authorization?

J1a. Waiver of requirement for written documentation of Consent

Will this research require a waiver of the requirement for written documentation of informed consent?

J2. Consent Procedures

Who will recruit subjects for this study?

Ы

PI's staff

Describe how research population will be identified, recruitment procedures, any waiting period between informing the prospective participant and obtaining consent, steps taken to minimize the possibility of coercion or undue influence and consent procedures in detail.

The research population will be identified by using email and verbal solicitation to solicit participants in the study from BCM emergency medicine residents, PA/NP fellows, and emergency medicine faculty members. Subjects that will be used as the model patients will be identified by verbal and electronic solicitation to the faculty members of the Emergency Medicine Department at Baylor College of Medicine. It will be made clear that participation in the study is voluntary and will not affect grading, assessment, or employment status of any participant.

Are foreign language consent forms required for this protocol?

Nο

J3. Privacy and Intrusiveness

Will the research involve observation or intrusion in situations where the subjects would normally have an expectation of privacy?

No

J4. Children

Will children be enrolled in the research?

No

J5. Neonates

Will non-viable neonates or neonates of uncertain viability be involved in research?

J6. Consent Capacity - Adults who lack capacity

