#### **Arms of the Study**

This study has two arms being compared. The first arm is the phased-array transducer arm, which collects the above mentioned outcomes for. The second arm is the curvilinear transducer arm. Each ultrasound operator will be randomized to one of the two arms to begin with. There will be no blinding of the participants or of the study investigators. After each participants completes their FAST ultrasound, they will cross-over to the other arm of the study. Thus, each participant will perform two FAST exams, one with each type of transducer.

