## **Statistical Analysis**

For the primary outcome of time to completion of the ultrasound exam, we will report descriptive statistics for each arm. We will report any differences between these descriptive statistics for each type of transducer. If there are enough participants in each subgroup to make meaningful comparisons, we may also report subgroup descriptive statistics based on the training level of the participants.

We will perform a t-test to analyze the two arms for differences in mean time to completion of each ultrasound. Additional subgroup comparisons based on the level of training of participants may be performed.

For the secondary analysis, Fisher's exact test will be used to determine if there is a statistically significant difference between the numbers of technically adequate for interpretation ultrasound exams performed for each arm. A numeric scale for quality of the images may also be used, and if so, a t-test to analyze differences in numeric scale rating of image quality between the two arms will be used.

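### Minor: transducer order is randomised without regard to training level and the time analysis has no period term, so an optional training-level result can absorb part of an order effect

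*Protocol*

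**What the plan says.** Protocol F1 (Design) states: "Participants will be block-randomized to a group A and group B". The SAP (Arms of the Study) adds: "Each ultrasound operator will be randomized to one of the two arms to begin with". Neither document gives a block size or a stratification factor. The SAP makes the design a two-period crossover: "Thus, each participant will perform two FAST exams, one with each type of transducer".

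Operators cover a wide range of experience. The inclusion criteria in F1 say: "Emergency medicine residents (PGY 1-3), emergency medicine PA fellows, and emergency medicine faculty at Baylor College of Medicine will be recruited as operators". The SAP (Study Outcomes) lists training level among the baseline data.

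On analysis, the SAP (Statistical Analysis) says: "We will perform a t-test to analyze the two arms for differences in mean time to completion of each ultrasound". It does not say whether the test is paired and includes no period or order term. On training level it says "we may also report subgroup descriptive statistics based on the training level of the participants", on condition that the subgroups are large enough, and then: "Additional subgroup comparisons based on the level of training of participants may be performed". Both statements are permissive. Neither document defines the levels or gives numbers per level.

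**The concern.** In a crossover, the randomised group determines the order of the two transducers. If operators tend to be faster (or slower) on their second timed exam, that period effect cancels from the transducer comparison only when equal numbers start with each transducer. Blocking keeps the order close to balanced over all operators. It does nothing to balance it within residents, advanced practice providers or faculty, or within a residency year.

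Training level is the one factor that the SAP singles out for subgroup reporting, and it is known before allocation. Leaving it out means that a small level can split unevenly by chance, and a t-test without a period term would then count part of the order effect as a transducer effect in that level. The split cannot be repaired by allocation once the data are in, although a period term can still adjust for it.

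**Working it through.** **Inputs.** From the documents: total size "Local: 40 Worldwide: 40" (G1, a convenience sample with no power calculation, so there is no planned figure to reproduce), two orders, and a t-test without a period term. Assumed, because the documents are silent: all 40 are operators, 20 start with each transducer, and the level sizes, practice gain and residual SD are as stated below.

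**1. Leak.** Let g be the time saved on the second exam and τ the true curvilinear minus phased-array difference. An operator who starts with the curvilinear probe has expected difference τ + g; one who starts with the phased array has τ − g. With nC and nP operators in the two orders of a level:

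mean difference = τ + g × (nC − nP)/(nC + nP).

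At 4:4 the leak is 0. At 5:3 it is 2/8 = 25% of g, and at 6:2 it is 4/8 = 50%. An assumed g of 60 s therefore gives 15 s at 5:3 and 30 s at 6:2.

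**2. Chance of an uneven split in a level of 8.** P(k start with the curvilinear probe) = C(20,k) × C(20,8−k) / C(40,8). This gives 0.305 for 4:4 and 2 × 0.230 = 0.460 for 5:3 in either direction. So P(not 4:4) = 0.695 and P(6:2 or worse) = 1 − 0.305 − 0.460 = 0.235. Simulated unstratified blocks of 2, 4, 8 and 10 give the same figure, so the unstated block size does not matter.

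**3. Other level sizes.** P(3:1 or worse) is about 60% in a level of 4 and 8% in a level of 12. The average absolute leak is 36% of g at 4 operators, 24% at 8, 19% at 12 and 12% at 20.

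**4. Chance that at least one level is split 3:1 or worse.** This depends heavily on the assumed levels:

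| Assumed level sizes | Chance |
|---|---|
| 8/8/8/4/12 | about 81% |
| 8/8/8/8/8 | about 68% |
| 8/8/8/4/12, level of 4 not reported | about 55% |
| 9/7/7/5/12 | about 53% |
| 24/12/4 (three operator types) | about 63% |
| 24/12/4, level of 4 not reported | about 8% |

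**5. Precision in a level of 8** (assumed g = 40 s, SD of the within-operator difference 40 s). The sampling part is 40/√8 = 14.1 s. The share (nC − nP)/8 has variance 4 × [8 × 0.25 × 32/39]/64 = 0.103, so the leak has SD 40 × √0.103 = 12.8 s. Together: √(14.1² + 12.8²) = 19 s without stratification, against 14 s with a 4:4 split.

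**6. Overall comparison** (levels 8/8/8/4/12 with assumed gains of 60/40/30/50/10 s). The mean gain is 1360/40 = 34 s, and the squared deviations sum to 13,760. The SD of the induced error is √[13,760 × (40/39)]/40 = 3.0 s.

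**7. False positives in a level of 8** (no true transducer difference, g of 40 or 60 s, SD 20 to 60 s, paired t-test, two-sided 5%, simulated). Unstratified without a period term: about 4%. The same, looking only at splits of 6:2 or worse: about 10% to 16%. Stratified 4:4 without a period term: about 0% to 2%. Stratified 4:4 with a period term: 5%.

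**The case against.** The strongest reply is that order is randomised. Over all possible allocations the leak averages to zero, and the plain test does not exceed its nominal error rate (about 4%), because a practice gain also widens the spread of the differences. This stands. The issue is precision, and interpretation once an uneven split has occurred; such a split would be visible in the data.

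Four stronger readings are tempting, and the documents do not support them.

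- A reader might infer that the SAP commits to comparing transducers within five training levels. It only permits such comparisons, makes the descriptive tables conditional on numbers, and defines no levels. Its Background names three operator types.
- A reader might infer that a badly split level is almost certain. The 81% depends on one assumed set of sizes that includes a level of 4; other plausible assumptions give 8% to 68%.
- A reader might infer that the primary result is compromised. Under the assumed gains the added error is about 3 s.
- A reader might take a practice gain, larger in junior residents, as established. Neither document gives one. Operators are described as trained, the second exam is on a different model patient, and no interval between exams is stated.

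It is also fair to say that a period term alone removes the leak at any split with at least one operator in each order. What remains for stratification is that it keeps the orders balanced in small levels and protects the simple descriptive tables, which carry no adjustment.

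**Conclusion.** The point holds as a minor improvement. Order is block-randomised without training level, and the SAP's time analysis has no period term, so an optional training-level estimate can carry part of an order effect when its level splits unevenly. For an assumed level of 8, a 6:2 or worse split has a chance of about 23%, and a 6:2 split passes half of the period effect into the estimate. There is no bias on average, and the overall comparison barely moves.

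These sizes rest on assumed level sizes, an assumed period effect, and 40 operators. G1 says 40 subjects, and the protocol also counts model patients in its study population, so the number of operators may be smaller. The study is a self-declared pilot and the affected analyses are optional, which limits the priority.

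**What to change.** 1. **Protocol F1.** State that operators are randomised to transducer order in small blocks, stratified by training level. Use the levels that will be reported: for example resident, advanced practice provider and faculty, or residency year if numbers allow. Blocks of 2 hold each level to within one operator of balance. Blocks of 4 can leave a 4:2 split in a level of 6, a leak of 2/6 = 33%.
2. **SAP, Statistical Analysis.** Analyse within-operator time differences with a period (order) term, overall and within each reported level. The estimate is then the simple average of the mean differences in the two orders. This must accompany the stratification: balanced orders with a plain t-test leave the standard error too large, as the 0% to 2% false-positive rate shows. The term costs one degree of freedom and needs at least one operator in each order.
3. **Group labels.** F1 and F2 define the first transducer of groups A and B in opposite ways. Reconcile these passages in the same edit, or the order term cannot be coded reliably.

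The cost is one allocation list per level, short edits to F1, F2 and the SAP, and some predictability of order in an unblinded study. The last matters little because every operator uses both transducers. These changes do not address a separate matter: as F1 is worded, each transducer appears tied to one model patient in both orders.

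### Protocol F1 switches transducer and model patient together, so with one pair of patients the transducer effect cannot be separated from the patient difference; F2 and the SAP do not settle it

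*Protocol*

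**What the plan says.** Protocol F1 (Design) sets the first exam: "Group A will conduct an ultrasound exam on one patient using a curvilinear transducer, and group B performs the exam on another different patient", group B using the phased-array transducer. It then sets the second: "they will cross-over, performing the same exam using the other transducer on the other patient". At crossover both the transducer and the person scanned change.

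Protocol F2 (Procedure) gives the opposite starting transducers: "Operators randomized to group A will perform an ultrasound exam on a patient using a phased-array transducer", while "operators randomized to group B will perform an exam on the other patient using a curvilinear transducer". For the second exam it says only: "After each subject in each group completes their FAST exam, they will cross-over". It does not say whether the patient changes.

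The SAP (Arms of the Study) defines its two arms by transducer alone and says of operators that "they will cross-over to the other arm of the study". It does not assign model patients to transducers or to order.

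No section states how many model patients there will be. Protocol G2 names transducer type as the only independent variable, and the SAP (Statistical Analysis) plans: "We will perform a t-test to analyze the two arms for differences in mean time to completion of each ultrasound". Adequacy is compared between transducers with Fisher's exact test. Neither analysis includes the patient.

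**The concern.** A crossover removes differences between operators because each operator uses both transducers. It does not remove differences between the people scanned unless each transducer is used on each of them. Under F1 with a single pair, transducer and patient are two names for the same split of the data.

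The two patients may differ in ways that affect scanning time and image quality. Protocol E2 admits both genders and ages 18 to 64, and the four views include the heart and the bladder. The only standardisation stated is a three-hour fast. One patient being easier to scan could produce a significant transducer result, or could cancel a real one. More operators on the same two patients would only estimate the wrong quantity more precisely.

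The study's single question (Section D) is whether transducer type affects speed or quality, and this defect cannot be repaired after the data are collected.

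**Working it through.** The plan has no power calculation (G1 describes 40 as a convenience sample), so there is no figure to reproduce.

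**Structure.** Let τ be the transducer effect (phased-array minus curvilinear), δ the patient difference (P2 minus P1) and ω the period effect (second exam minus first). The operator's own level cancels in each within-operator difference, phased-array minus curvilinear:

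| Design, one pair of patients | Sequence | Expected difference |
|---|---|---|
| F1 | A: curvilinear/P1, then phased/P2 | τ + δ + ω |
| F1 | B: phased/P2, then curvilinear/P1 | τ + δ − ω |
| F2, patient kept | A: phased/P1, then curvilinear/P1 | τ − ω |
| F2, patient kept | B: curvilinear/P2, then phased/P2 | τ + ω |

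Under F1 the average over groups is τ + δ. Half the difference between groups gives ω, and nothing gives τ alone. If F2 is read with F1's rule, the result is the same with the sign of δ reversed. If the patient is kept, the average is τ.

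The design matrix confirms this (intercept, transducer, patient, period; 80 exams by 40 operators, 20 per group):

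- F1: rank 3 of 4, transducer-patient correlation +1.
- F2 labels with F1's rule: rank 3 of 4, correlation −1.
- Patient kept: rank 4, correlation 0.

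With operator effects added, F1 has rank 42 with or without the transducer column, so transducer remains inestimable given patient.

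**Illustration for time.** These inputs are assumptions: two-sided 5% level, 40 operators, no transducer effect, patient difference of d SDs of exam time, within-operator correlation ρ. The SD of the within-operator difference is √(2(1 − ρ)), which is 1 at ρ = 0.5. The noncentrality of the paired t-test is d√40 / √(2(1 − ρ)). For d = 0.5 and ρ = 0.5 it is 0.5 × 6.325 / 1 = 3.162; against a critical value of 2.023 (39 df) the rejection rate is 86.9%.

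| Patient difference | Paired, ρ = 0.5 | Paired, ρ from 0.3 to 0.7 | Unpaired, ρ = 0.5 |
|---|---|---|---|
| 0.25 SD | 34% | 26–51% | 12% |
| 0.5 SD | 87% | 74–98% | 63% |
| 0.75 SD | >99% | 97% to ~100% | 97% |

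Both t-tests are shown because the SAP does not say which is meant. If the 40 includes two model patients, leaving 38 operators, the paired rates at ρ = 0.5 are 32%, 85% and 99%. When each operator keeps the same patient, the paired test stays at about 5% whatever the patient difference.

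**Several pairs under F1's rule.** Here the patients are random, with an assumed between-patient SD of 0.3, so the difference within a pair has SD 0.3 × √2 = 0.42. With ρ = 0.5 the paired rate is about 49% for one pair, 33% for 2, 21% for 4, 10–11% for 10 and 7% for 20. These figures form their own scale and should not be set against the fixed differences in the table above.

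**Adequacy.** Fisher's exact test was enumerated for 40 versus 40 exams treated as independent, with no transducer effect. If both patients yield 90% adequate exams it rejects in 1.7% of trials; at 90% versus 80%, in 16%; at 90% versus 70%, in 53%.

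**The case against.** The strongest reply is that complete confounding needs a single pair, and the documents never give the number of model patients. Protocol F1 and J2 refer to faculty volunteers in the plural, Section P lists three ultrasound machines, and the pair described in F1 could be the two people a given operator meets. That is fair, and the conclusion is conditional on it. But more pairs under the same rule only dilute the problem, and no section plans to rotate transducers across patients.

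It can also be said that F2 and the SAP are merely silent, so F2's crossover is shorthand for F1's. If so, F1's rule governs throughout and the confounding applies in full. The reversed group labels in F2 have no bearing on it.

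The illustrative rates rest on assumed inputs. The Fisher figures also need an exam-level adequacy rule, which the protocol does not give (it grades each view), and they ignore pairing. All of this stands, but the structural result uses none of those inputs.

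Keeping each operator on one patient would also make the transducer effect estimable, without a patient term. That is a legitimate alternative, although the second scan is then a repeat on a now familiar patient.

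Finally, the study is labelled a pilot. G2 nonetheless plans significance tests meant to support or refute the hypothesis.

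**Conclusion.** The concern holds. Followed as written with one pair of model patients, F1 yields transducer effect plus patient difference for both the primary and the secondary outcome, and no covariate, paired test or larger number of operators can separate them. This follows from the allocation rule alone.

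The size of the error is unknown because the documents give no SD, correlation or patient difference. Under the stated assumptions, even a quarter of an SD between the two patients raises the paired false-positive rate from 5% to about 34% (26–51% over correlations of 0.3 to 0.7). With several pairs the confounding is partial. F2 and the SAP leave open a reading in which the effect is estimable, so the sections must be reconciled before the first operator is randomised.

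**What to change.** State the number of model patients, and replace the allocation text in F1 and F2 with one table. Block-randomise operators, about 10 to each, to four sequences:

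| Sequence | First exam | Second exam | Expected difference (phased − curvilinear) |
|---|---|---|---|
| 1 | curvilinear on P1 | phased on P2 | τ + δ + ω |
| 2 | phased on P2 | curvilinear on P1 | τ + δ − ω |
| 3 | curvilinear on P2 | phased on P1 | τ − δ + ω |
| 4 | phased on P1 | curvilinear on P2 | τ − δ − ω |

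The average of the four is τ. The design matrix has rank 4 and transducer-patient correlation 0. If more than one pair is used, apply the table within each pair. Repeat it in the SAP under Arms of the Study so that crossover has one meaning.

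Analyse time within operator with a patient term; the simulated false-positive rate is then 5%. Without that term the paired t-test is unbiased but conservative (about 4%, 3% and 1.5% at patient differences of 0.25, 0.5 and 0.75 SD). For adequacy, each transducer is then used about equally often on each patient, so the comparison is no longer tied to one person.

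One limit should be stated: with two patients and operator effects fitted, a transducer-by-patient interaction cannot be estimated, so the result is an average over that pair.

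The cost is revised text in F1, F2 and the SAP, a new randomisation list, one model term, and swapping transducers between stations. No operators, patients or exams are added.
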